Men's Sexual Risk Behaviors: Alcohol, Sexual Aggression, and Emotional Factors

NCT: Not Yet Assigned

Date: March 18, 2019

Study Protocol and Statistical Analysis Plan

Study Protocol

The objectives of the protocol are to examine men's sexual risk intentions and sexual risk behaviors, with a focus on the contributing roles of sexual aggression propensity, alcohol intoxication, and emotions. The study will involve 3 phases: 1) a baseline survey; 2) a 30-day daily diary assessment of emotions, drinking and sex coping motives, and drinking and sexual behavior; and 3) a laboratory experiment assessing the effects of alcohol intoxication and provocation on in-the-moment emotional state and sexual risk behavior/condom use resistance likelihood.

Recruitment. Participants will be recruited from the community through advertisements placed in online classifieds, social networking websites, community newspapers, and local venues that target the young adult population. Ads will state that single men 21-30 years old are needed for an Arizona State University study of alcohol and male-female relationships. We will also use flyers, brochures, and postcards in locations likely to reach young single men, such as local community colleges, coffee shops, and bars. All advertising materials will include a URL for a website that will provide limited information about the study with particular emphasis on information about the PI and research at Arizona State University. If they are interested in proceeding, potential participants will need to call our offices for more detailed information, screening, and scheduling.

Retention. We will take multiple steps to retain participants throughout the project. First, we will reduce the time span between the three study phases as much as possible during scheduling such that all three phases of the study will take less than 6 weeks total. Second, we will make participation as convenient as possible by using online data collection for the baseline and daily diary surveys. We will also offer transportation assistance (e.g., bus passes, taxi rides home) for the in-lab experiment. Third, we will give reminders to participants if more than 2 days have passed without completion of the baseline survey or if they miss more than 2 consecutive daily assessments. Finally, we will structure our payment and incentive schedule to encourage full completion. Similar procedures and incentives have yielded retention rates of 87-92% over 3-month periods in our prior studies.

Study Design. All participants will complete an online baseline survey that will assess information about sexual risk behavior, drinking behavior, sexual aggression, and emotion regulation skills. The online daily diary study will require participants to answer questions once a day during a 30-day period assessing their emotions, sexual risk behaviors, and drinking behaviors. During the in-lab experiment, two factors will be manipulated between subjects: alcohol intoxication and provocation condition. We will use a randomized block design to assign participants to experimental conditions based on their sexual aggression history so that aggression backgrounds are evenly distributed across the cells. Participants will receive either no alcohol (control beverage) or a high alcohol dose (target peak BAC = .08%), will experience a standard experimental provocation manipulation (high vs. none), and then will read a sexual risk analogue and rate their sexual risk intentions while on the ascending limb of the BAC curve.

Statistical Analysis Plan

Sexual Risk Behavior. For the sexual risk behavior outcome, we plan to enroll 420 subjects. Sexual risk behavior will be assessed in multiple ways: having unprotected vaginal or anal sex (yes/no), condom use resistance (yes/no), and partner type (casual vs. steady). GLMMs with a negative binomial distribution and log link function will be used to examine the daily influence of emotions on alcohol consumption, and a binomial distribution and logit link function will be used to examine the daily influence of emotions on the binary indicators of sexual risk behavior. Multilevel mediation (MLM) will be conducted to examine the potential mediating effects of drink- and sex-to-cope motives on the relation between emotions and subsequent alcohol use and sexual risk behavior. The moderating effects of sexual aggression propensity and emotion dysregulation will be examined by creating interaction terms with daily emotions and will be entered in the GLMM models described above.

Sexual Risk Intentions. For the sexual risk intentions outcome, we plan to enroll 420 subjects. The sexual risk intentions variables will include unprotected sex and CUR intentions, and the between-subjects factors will be intoxication and manipulated provocation. Direct and indirect effects of alcohol intoxication (.08% vs. control) and provocation (high v. none) will be tested utilizing path analysis within a structural equation modeling (SEM) framework, which provides significance tests and confidence intervals for total indirect effects and specific indirect effects. A path analysis will be conducted to test whether alcohol intoxication directly increases sexual risk intentions and whether emotional state mediates the effects of provocation and alcohol intoxication on sexual risk intentions. To test the hypothesis that the effects of intoxication and provocation on negative emotional states will be greater among those with stronger sexual aggression perpetration propensities, SEM analyses that include that interaction term will be conducted. Additional SEM analyses will be conducted to test the moderating effects of emotion dysregulation on the negative emotion-sexual risk intentions relationship.

Power and Sample Size. The study was powered to detect the mediational effects of negative emotional state and on the relationship between provocation and alcohol intoxication on unprotected sex likelihood, as this hypothesis serves as a test of the overarching conceptual model and requires participants be randomized to one of four experimental conditions, thereby decreasing power. Monte Carlo simulations indicate that a sample size of 350 yields power .79 - .96 to detect small to medium effects. Based on an estimated 20% attrition rate, the final sample recruited will comprise 420 men. This sample size also yields sufficient power to detect small to medium effects in the within-subject GLMM analyses examining men's daily sexual risk behavior.

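### Must the plan fix which diary days enter the daily unprotected-sex model, and add a model for whether sex occurred?

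*Combined protocol and SAP*

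**What the plan says.** The Study Protocol describes the second phase as "a 30-day daily diary assessment of emotions, drinking and sex coping motives, and drinking and sexual behavior". Under Study Design, men "answer questions once a day during a 30-day period assessing their emotions, sexual risk behaviors, and drinking behaviors". Days without sex will therefore be in the data.

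The Sexual Risk Behavior section of the SAP names three daily indicators: "having unprotected vaginal or anal sex (yes/no), condom use resistance (yes/no), and partner type (casual vs. steady"). A binomial mixed model with logit link is to be "used to examine the daily influence of emotions on the binary indicators of sexual risk behavior". The only other daily outcome model is for drinking: "GLMMs with a negative binomial distribution and log link function will be used to examine the daily influence of emotions on alcohol consumption". The same section plans multilevel mediation for the "potential mediating effects of drink- and sex-to-cope motives on the relation between emotions and subsequent alcohol use and sexual risk behavior", and enters moderator interactions into the same mixed models.

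No section states which diary days enter each binary model, how a day without sex is coded, or any model with sex occurrence as its outcome. Power and Sample Size says only "This sample size also yields sufficient power to detect small to medium effects in the within-subject GLMM analyses", with no day count or event rate.

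**The concern.** A once-daily yes/no variable for unprotected sex can be read in two ways. If every diary day enters and days without sex are scored *no*, abstinence and protected sex share a category. The odds ratio for emotion could then come from more frequent sex, from less condom use, or from opposite effects on the two. If only days with sex enter, the odds ratio describes condom non-use given sex, and the plan is silent on whether emotions change the occurrence of sex.

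Two analysts following the text could estimate different quantities from very different numbers of records. The mediation and moderation models would inherit the choice. Sex-to-cope motives could well act through having sex, and no planned model would show that route. At stake is what a diary result may be said to mean.

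**Working it through.** The documents give no figure for the daily models to reproduce, so the check is of the mechanism. All rates below are assumptions.

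**Formula.** Let s be the chance of sex on a day and c the chance that it is unprotected given sex. With days without sex coded *no*, P(unprotected sex) = s × c, and

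all-days OR = odds(s₁c₁) / odds(s₀c₀).

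**Worked case, s₀ = 0.15, c₀ = 0.5.** Baseline: 0.15 × 0.5 = 0.075, odds 0.0811.

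- Sex OR 1.5, no condom effect: s₁ = 0.2093; product 0.1047, odds 0.1169; OR = 0.1169/0.0811 = 1.44.
- Condom non-use OR 1.5, no sex effect: c₁ = 0.6; product 0.090, odds 0.0989; OR = 1.22.
- Sex OR 1.5 with condom non-use OR 0.8: c₁ = 0.444; product 0.0930, odds 0.1026; OR = 1.26, above 1 although condom non-use given sex falls.
- Solving for an all-days OR of 1.20: sex OR 1.22 alone, or condom non-use OR 1.45 alone.

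**Ranges for s₀ from 0.05 to 0.30 and c₀ from 0.4 to 0.8.**

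| Effect on sex (OR) | Effect on condom non-use (OR) | All-days OR |
|---|---|---|
| 1.5 | 1.0 | 1.36–1.49 |
| 1.2 | 1.0 | 1.15–1.20 |
| 1.0 | 1.5 | 1.08–1.29 |
| 1.5 | 0.8 | 1.16–1.42 |

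**Records.** 420 men × 30 days = 12,600 possible diary days. At 5% to 30% sex days this leaves 630 to 3,780 for a sex-days model, before any missed entries.

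**What the suggested extra models would deliver.** The suggestion is a model for any sex on all days and one for unprotected versus protected sex on sex days. The sex-days model was simulated as a random-intercept logistic model with 336 men (420 × 0.8), 24 completed days (30 × 0.8, assumed), person SD 1.0, a standard-normal daily emotion, and sex on 5/15/30% of days.

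- Power for OR 1.2 is .28/.79/.98 if 50% of sex is unprotected, and .17/.39/.72 if 10% is.
- With no shared unmeasured cause, a true null is rejected in about 5% of runs. If an unmeasured day-level factor raises both sex and condom non-use by 1.0 log-odds per SD, and emotion has OR 1.5 on sex, the sex-days OR is 0.97/0.95/0.95 when the truth is 1.0. It is then significant in 5.5/9.8/23% of runs.
- Two further independent tests at .05 carry a chance of 1 − 0.95² = 9.75% of at least one false positive per emotion variable. The plan speaks of emotions in the plural without a count. Two would give 1 − 0.95⁴ = 18.5%, and five would give 1 − 0.95¹⁰ = 40.1%.

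**The case for a change.** The strongest case for a change is that an outcome's denominator is basic content for an SAP, and one sentence per outcome would supply it. Leaving the day set open until data are seen gives analysts a freedom that a plan should remove. The power claim for the daily models cannot be judged without knowing the days it assumes. Because sex-to-cope motives are a planned mediator, whether emotions act through having sex is close to the study's own interest.

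Much of this stands as description. The rule is unwritten, and neither redaction nor text extraction explains the gap. The two readings do give different estimands, and a line recording the choice would do no harm.

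It does not show that the plan goes wrong. Either reading gives an interpretable result. With days without sex coded *no*, a significant odds ratio reflects a true effect on exposure; with sex days only, the blending is gone. The misleading case needs both the all-days coding and a report worded as condom behaviour, and the plan states neither. Partner type has no value on a day without a partner, so analysts must already decide eligible days outcome by outcome, with the diary items in front of them. Whether emotions alter the occurrence of sex is a worthwhile question, but no stated hypothesis asks it.

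**Conclusion.** The gap is real but is missing detail that analysts would settle sensibly, so no change to the plan is needed. Under the all-days coding, the algebra shows that one odds ratio can arise from different mixtures: 1.36–1.49 from a sex effect of 1.5 alone, and 1.16–1.42 even when condom non-use falls. That limits how the result may be worded; it does not make the estimate invalid. These sizes rest on assumed rates of sex (5–30% of days) and of unprotected sex (40–80% of it), and show the mechanism, not a likely error in this study.

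The two-part split is optional, and statisticians could differ on it. It separates the two routes, but at the price of more tests, power as low as .17–.28 for OR 1.2 when sex occurs on 5% of days, and exposure to selection on sex days. The issue is confined to the observational diary phase. The randomised laboratory mediation analysis, for which the study was powered, does not depend on it.

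### The path model for the powered mediation hypothesis names no baseline covariates, leaving its emotion-to-intentions path and indirect effects open to confounding

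*Combined protocol and SAP*

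**What the plan says.** Power and Sample Size names the hypothesis that drove the sample size: "The study was powered to detect the mediational effects of negative emotional state". Sexual Risk Intentions gives the model that tests it: "A path analysis will be conducted to test whether alcohol intoxication directly increases sexual risk intentions and whether emotional state mediates the effects". For that outcome, "the between-subjects factors will be intoxication and manipulated provocation". No baseline covariate is listed, and the section neither states an assumption about mediator-outcome confounding nor plans a sensitivity analysis for it.

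Study Design shows what is randomised: "two factors will be manipulated between subjects: alcohol intoxication and provocation condition". Allocation is blocked: "We will use a randomized block design to assign participants to experimental conditions based on their sexual aggression history". All men complete an "online baseline survey that will assess information about sexual risk behavior, drinking behavior, sexual aggression, and emotion regulation skills".

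Two of these traits return in separate models. One SEM tests whether "the effects of intoxication and provocation on negative emotional states will be greater among those with stronger sexual aggression perpetration propensities". The other is described thus: "Additional SEM analyses will be conducted to test the moderating effects of emotion dysregulation on the negative emotion-sexual risk intentions relationship". Neither is named as the mediation test. Baseline sexual risk behavior and drinking appear in no intentions model.

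**The concern.** An indirect effect is the product of a factor-to-emotion path (a) and an emotion-to-intentions path (b). Randomisation protects a and the total effects. It does not protect b, because men arrive at their emotional state partly through their own dispositions. A trait that raises both negative emotion and risk intentions produces a b without any causal link between the two.

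Blocking does not help. It makes aggression history equally common in the four cells, but within each cell men with and without that history may still differ in both emotion and intentions. The plan's own theory makes aggression propensity a candidate confounder. It is expected to alter emotional responses to the manipulations, and the protocol's objectives list it as a contributor to risk intentions.

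At stake is the hypothesis that sized the study. Where a factor shifts emotion, a confounded b can create mediation that is not there. If a trait acts in opposite directions on emotion and intentions, it can hide mediation that is.

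**Working it through.** **Inputs from the documents.** A 2×2 between-subjects design; N = 350 in the power statement; 420 recruited with 20% attrition, which leaves 420 × 0.80 = 336.

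**Assumed inputs.** Two-sided 5% level; least-squares path equations; alcohol shifts emotion by 0.2 SD and provocation by 0.5 SD; SD net of the factors equal to 1; 40% of men with an aggression history; trait loadings as shown. None of these is in the documents.

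**The plan's own figure.** Power of .79 to .96 at N = 350 cannot be reproduced, because no path coefficients, significance level or test of the indirect effect are given. With a joint-significance test, standardised paths of 0.15 and 0.20 give 0.78, and 0.20 and 0.25 give 0.965. The range is therefore attainable, but only this check's unconfounded case has been examined.

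**Step 1: false positives for b by residual correlation.** Let true b = 0 and let r be the emotion-intentions correlation that shared traits leave, net of the factors. The t test of b has df = N − 4 and noncentrality r·√df / √(1 − r²). For r = .06 and N = 336: .06 × √332 / √(1 − .0036) = .06 × 18.22 / .998 = 1.10, which gives 19%.

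| r | N = 336 | N = 350 |
|---|---|---|
| .02 | 6.5% | 6.6% |
| .03 | 8.5% | 8.6% |
| .06 | 19% | 20% |
| .10 | 45% | 46% |
| .15 | 79% | 80% |

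**Step 2: from traits to r.** Let h be the SD shift for men with an aggression history and d the loading on standardised dysregulation. Then r = 0.4 × 0.6 × h(emotion) × h(intentions) + d(emotion) × d(intentions). For h = 0.3 and d = 0.2 on both: .24 × .09 + .04 = .062.

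**Step 3: simulation.** Block-randomised 2×2, N = 336, 3,000 replicates, true b = 0, equal loadings on emotion and intentions. Entries are rejection rates for b by covariates included.

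| h / d | implied r | none | dysregulation only | block + dysregulation |
|---|---|---|---|---|
| 0.2 / 0.1 | .020 | 6.3% | 5.4% | 5.2% |
| 0.3 / 0 | .022 | 6.5% | 6.7% | 4.7% |
| 0.3 / 0.1 | .032 | 9.1% | 6.9% | 5.1% |
| 0.5 / 0 | .060 | 18.8% | 18.4% | 4.9% |
| 0.3 / 0.2 | .062 | 21.2% | 7.2% | 4.4% |
| 0.3 / 0.3 | .112 | 52.6% | 6.6% | 5.1% |
| 0.5 / 0.3 | .150 | 79.3% | 22.5% | 5.2% |

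Fixing the residual SD at 1 instead lowers the last two unadjusted rates to 44.9% and 66.7%.

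**Step 4: other patterns.**

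- Unequal same-sign loadings: 10.4% to 23.2% unadjusted, 4.7% to 5.2% with block and dysregulation.
- Traits tied to emotion only: 4.2%, so no excess.
- The two traits confounding in opposite directions: 6.3% to 6.8%.
- Masking, true b = 0.2: power for b is 94.5% without confounding. If both traits act in opposite directions on emotion and intentions, it falls to 71.3% (loadings 0.3 / 0.2) or 85.9% (0.3 / 0.1). Adjustment restores about 95%.

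**Step 5: the indirect and direct effects.** Under the joint-significance test and equal loadings, a false indirect effect is declared in 6.3% to 79.2% of replicates for provocation and 2.5% to 36.3% for alcohol. Adjusted rates are 4.4% to 5.2% and 2.0% to 2.6%. Direct-effect bias is about −a × (bias in b), at most 0.2 × .15 = .03 SD for alcohol and 0.5 × .15 = .075 SD for provocation. The simulated ranges are −.004 to −.033 and −.008 to −.072.

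**Separate check.** One standardised trait with equal loadings of 0.1, 0.2, 0.3 and 0.4, N = 350, standardised a = 0.2, true b = 0. Path b is estimated at .01, .04, .10 and .17, and a false indirect effect is declared in about 5%, 12%, 42% and 85% of 2,000 replicates. With the trait in the model the rate is 4% to 6%.

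**The case against.** The strongest reply is that this is an argument from silence. The SAP is a short summary that writes out no full equation, so covariates may be intended. That is fair, and the unadjusted rates describe the model as worded, not one the plan firmly commits to. But covariates that are intended still have to be named in advance.

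Second, the dysregulation SEM addresses the emotion-intentions relationship. With its main effect included, as is usual though not stated, it would reveal part of any bias. In ten of the twelve same-sign and emotion-only scenarios, adjusting for dysregulation alone brings the false-positive rate to 7.4% or less. The two exceptions (18.4% and 22.5%) assume a 0.5 SD aggression-history shift in both emotion and intentions. This stands as partial cover, but that SEM is not the planned mediation test. The aggression SEM is described for effects on emotion, not for the intentions equation.

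Third, the false-positive rates for b overstate the alcohol indirect effect, which is below 5% in the weak cases. That is correct, and it depends on the assumed 0.2 SD alcohol path. The match between b and the provocation indirect effect likewise depends on the assumed 0.5 SD.

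Fourth, every loading is assumed, and the highest rates need strong same-sign loadings on both variables. The documents cannot say which case applies.

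Fifth, adjustment is not a full cure. A further unmeasured common cause loading 0.1, 0.2 or 0.3 on both variables still gives about 5-6%, 11% or 32-38% false positives for b.

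Finally, the statement that total effects and factor-to-emotion paths are unbiased assumes that losses after randomisation are ignorable.

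**Conclusion.** The concern holds. As worded, the model that tests the powered hypothesis leaves path b and the indirect effects open to confounding by traits the study measures, and neither blocking nor the separate SEMs closes the gap. Total effects and factor-to-emotion paths are not affected, and bias in the direct effects is small.

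The size is unknown. With equal same-sign loadings, the false-positive rate for b is 6-9% when they are weak, 19-21% when moderate and 45% or more when strong, against about 5% after adjustment. The case for changing the plan rests on the low cost of adjustment and the central place of this hypothesis, not on the largest of these rates. The change should be made; confidence is moderate because all the loadings are assumed.

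**What to change.** In the main path model, regress emotional state and both intentions outcomes on aggression history (the randomisation block) and baseline emotion dysregulation, alongside intoxication and provocation. Preferably add baseline sexual risk behavior and drinking from the same survey. Name the adjusted indirect effects as the test of mediation.

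The two further covariates can matter. If those traits each load 0.2 on both variables, added to the 0.2 / 0.1 case, the false-positive rate for b is 44.2% unadjusted, 30.9% with block and dysregulation, and 4.9% with all four. At loadings of 0.1 the rates are 11.0%, 6.4% and 5.2%.

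State the assumption of no unmeasured mediator-outcome confounding. Report how large a residual emotion-intentions correlation would remove the indirect effect. Mean diary emotion is at most an optional sensitivity analysis, since it depends on phase order and diary completeness; it was not simulated.

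The cost is SAP wording, a little analysis and no new data. Two irrelevant covariates left power for b = 0.2 at 94.4% against 94.5%. Four, at one degree of freedom each, reduce residual df from 332 to 328, which widens standard errors by a factor of about √(332/328) = 1.006.

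### The power range of .79-.96 is quoted at 350 men, but the plan's own enrolment and attrition leave 336, and the range cannot cover effects as small as d = 0.20 on the randomised-factor path

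*Combined protocol and SAP*

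**What the plan says.** The Power and Sample Size section sizes the study on one hypothesis: "The study was powered to detect the mediational effects of negative emotional state", acting between the two experimental factors and the likelihood of unprotected sex. The plan notes that this hypothesis "requires participants be randomized to one of four experimental conditions, thereby decreasing power". The power claim is: "Monte Carlo simulations indicate that a sample size of 350 yields power .79 - .96 to detect small to medium effects". Enrolment follows: "Based on an estimated 20% attrition rate, the final sample recruited will comprise 420 men".

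Under Study Design, "two factors will be manipulated between subjects: alcohol intoxication and provocation condition", each at two levels. Under Sexual Risk Intentions, the mediation is tested by path analysis in an SEM framework, "which provides significance tests and confidence intervals for total indirect effects and specific indirect effects".

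The plan does not give the path coefficients or standardised differences that were simulated, the alpha level and sidedness, or the type of test or interval for the indirect effect.

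**The concern.** Two things do not fit together.

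- **Sample size.** The power is quoted for 350 men, but the enrolment and attrition in the next sentence leave fewer. The figure that justifies the study is for a sample the plan does not expect to have.
- **Effect size.** A power range attached to effects running from small to medium is easily read as .79 for a small effect and .96 for a medium one. Each mediated effect starts from a two-level between-subjects factor, so its first path compares about 175 men with 175. That comparison has less than even power at the conventional small difference of d = 0.20, and a strong second path cannot make up for a weak first one.

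This is the only quantitative basis for the sample size, and the plan treats the hypothesis as the test of its whole conceptual model. If mediation is not found, the stated power governs how far a small mediated effect can be considered ruled out.

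**Working it through.** **Inputs from the plan.** Simulated N = 350; stated power .79 to .96; 420 enrolled; 20% attrition; two crossed two-level factors.

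**Assumptions, because the plan is silent.** Equal allocation to the four cells, two-sided alpha .05, no covariates, and a conventional small difference of d = 0.20 (r about .10). A first path of .14 (d about 0.28) is also shown.

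**Step 1: retained sample.**
- 420 × (1 − 0.20) = 336.
- Enrolment needed to keep 350: 350 / (1 − 0.20) = 437.5, so 438.
- The plan's 420 equals 350 × 1.20. It leaves 350 only if attrition is 1 − 350/420 = 16.7%.

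**Step 2: can the plan's range be reproduced?** Not directly, since no effect size is given. Solving backwards for the first path at 175 per level, d = (1.960 + z) / √(175/2):
- power .79: (1.960 + 0.806) / 9.354 = 0.296
- power .96: (1.960 + 1.751) / 9.354 = 0.397

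**Step 3: first-path power.** Power ≈ Φ(d√(n/2) − 1.960), with n men per level. For d = 0.20:
- n = 175: Φ(1.871 − 1.960) = .464 (noncentral t: .463)
- n = 168: Φ(1.833 − 1.960) = .449 (noncentral t: .447)

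Noncentral t results:

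| d | r | N = 350 | N = 336 |
|---|---|---|---|
| 0.20 | .10 | .463 | .447 |
| 0.28 | .14 | .743 | .725 |
| 0.30 | .15 | .799 | .783 |
| 0.40 | .20 | .962 | .955 |
| 0.50 | .24 | .997 | .995 |

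**Step 4: power for the indirect effect.** Simulation of the 2×2 design at N = 350, 2,000 replicates:

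| First path d | Second path b | Both paths significant | Monte Carlo interval for a×b |
|---|---|---|---|
| 0.20 | .10 | .22 | .19 |
| 0.20 | .30 | .46 | .51 |
| 0.20 | .50 | .45 | .44 |
| 0.28 | .14 | .53 | .52 |
| 0.30 | .30 | .81 | .81 |
| 0.40 | .30 | .96 | .96 |

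At d = 0.20 with a strong second path, percentile and bias-corrected bootstrap intervals also stay within about .46 to .53. With b = .30 the second path is almost always significant, so joint power at 336 is essentially the first-path figure in Step 3.

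**Step 5: what would bring d = 0.20 up to .79 at N = 350?**
- One-sided .05 raises first-path power only to .59.
- Covariates would have to explain 1 − (0.20/0.296)² = about 54% of the variance in emotional state. The analysis plan describes no covariate adjustment for this model.

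**The case against.** The strongest reply is that the plan never says d = 0.20 was simulated. Small to medium can fairly mean sizes between the two benchmarks, and on that reading the range is attainable: d of about 0.30-0.40 with a second path of .30 gives roughly .81 to .96 at N = 350. Other pairs fit as well. A first path of d = 0.50 with a second path of .15-.20 gives about .80 to .96, and two equal paths of about .17 to .21 give much the same. The plan also does not say whether the label describes the first path, the second path or their product. All of this stands.

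A reader might therefore infer too much in two ways:
- **That the stated power is simply wrong.** The documents do not support this. With no effect size stated, there is no input for the figure to contradict. The first path is also an exact ceiling only when both paths must be significant; for interval tests it is approximate (.51 against .46 in one setting).
- **That the simulation must have used paths of .17 to .21.** That band follows only if the two paths are set equal, which the plan does not say.

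It can also be said that attrition may be milder than 20%. The Retention section reports 87-92% retention in earlier studies, and 420 × 0.87 = 365 would exceed 350. But the sample size calculation adopts 20%, and on that assumption 350 is not met.

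**Conclusion.** The point holds in two parts.

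1. **Unconditional.** On the plan's own enrolment and attrition, 336 men remain, 14 fewer than the number for which .79-.96 is quoted. The consequence is small: at d = 0.30 first-path power goes from .80 to .78, and at d = 0.40 it stays at .96 after rounding.
2. **Conditional on what small means.** If it includes d = 0.20 on the randomised-factor path, the lower bound of .79 is not attainable at either sample size. First-path power is .45 to .46, and indirect-effect power is about .2 with a weak second path and about .5 at most with a strong one. If the simulated effects lay between small and medium, the range is credible at 350 and needs only a slight downward revision at 336.

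These figures assume equal allocation, a two-sided .05 test and no covariates. One-sided testing does not change the conclusion at d = 0.20; covariates explaining about half or more of the variance in emotional state would.

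**What to change.** In the Power and Sample Size section:

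- Rerun the existing Monte Carlo simulation at N = 336 and quote that range.
- State the two path values behind each end of the range, the alpha level and sidedness, and the test or interval used for the indirect effect.
- Limit the claim to the effect sizes simulated and do not describe it as covering small effects. Add the power at first paths of .10 and .14, so that a reader can see what the study would probably miss.
- Take the path values from the simulation itself. Do not insert values worked back from the power figures, such as the .17-.21 band.

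The cost is a rerun and a few sentences. Enrolment need not change. The downside is that the stated power becomes slightly less favourable.

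### The sample-size figures do not fit together: 420 recruited with 20% attrition leaves 336 men, not the 350 on which the stated power rests

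*Combined protocol and SAP*

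**What the plan says.** The Power and Sample Size section says the study was sized for the mediation hypothesis in the laboratory experiment: whether negative emotional state carries the effects of provocation and alcohol on the likelihood of unprotected sex. It chose this hypothesis partly because it "requires participants be randomized to one of four experimental conditions, thereby decreasing power".

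The section then gives two figures in consecutive sentences. The power: "Monte Carlo simulations indicate that a sample size of 350 yields power .79 - .96 to detect small to medium effects". The recruitment number: "Based on an estimated 20% attrition rate, the final sample recruited will comprise 420 men".

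The Sexual Risk Intentions section of the SAP confirms that 420 is the number entering the study, not the number left at the end: "For the sexual risk intentions outcome, we plan to enroll 420 subjects".

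The Retention section of the protocol gives two facts that bear on attrition. The sponsor plans that "all three phases of the study will take less than 6 weeks total", and reports past experience: "Similar procedures and incentives have yielded retention rates of 87-92% over 3-month periods in our prior studies".

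**The concern.** Attrition is normally the share of those recruited who are lost. On that reading the plan's own rate does not bring 420 recruits down to 350 completers, and nothing in the documents gives the 20% another meaning, says that the 350 already allows for losses, or says that fewer than 350 would do.

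The published power range is therefore attached to a sample size that the plan does not expect to reach. A reader cannot tell whether the sponsor expects 336 or 350 men in the laboratory analysis, or 20% or about 17% attrition. The hypothesis affected is the one that set the sample size. The laboratory visit is the last of three phases, so men lost during the survey or the diary contribute no laboratory outcome.

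The concern is confined to that laboratory analysis. It does not extend to the separate statement about power for the daily-diary models.

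**Working it through.** **Inputs**

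- Sample size behind the stated power: 350 (Power and Sample Size)
- Stated power at 350: .79 to .96 (Power and Sample Size)
- Attrition: 20% (Power and Sample Size)
- Number recruited: 420 (Power and Sample Size; repeated under Sexual Risk Intentions)
- Experimental conditions: 4 (Power and Sample Size)
- Retention in prior studies: 87–92% (Retention)

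**Step 1. Reproduce the plan's figure.** Adding 20% to the target gives 350 × (1 + 0.20) = 420, an exact match. This is evidently how 420 was obtained.

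**Step 2. Apply the stated attrition to the recruited number.** 420 × (1 − 0.20) = 336. The shortfall is 350 − 336 = 14 men, and 14 / 350 = 4.0%. If the four cells are equal in size (the allocation ratio is not stated), that is 336 / 4 = 84 per cell against 350 / 4 = 87.5.

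**Step 3. Recruitment that 350 completers would need.** 350 / (1 − 0.20) = 437.5, rounded up to 438, which is 18 more than 420.

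**Step 4. Attrition at which 420 does give 350.** 1 − 350 / 420 = 16.7%; exactly, no more than 70 of 420 men lost.

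**Step 5. Approximate power at 336.** The simulation cannot be rerun from the documents: they give no alpha, path coefficients, mediation test or simulation model. The stated power can be scaled instead, taking the noncentrality as proportional to √N and assuming a two-sided alpha. For a single coefficient:

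power at N = Φ[(z_p + z_α) × √(N / 350) − z_α], where z_p is the normal quantile of the power at 350. At alpha .05, z_α = 1.960, and √(336 / 350) = 0.980.

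- From .79: (0.806 + 1.960) × 0.980 − 1.960 = 0.751, so power ≈ .774.
- From .96: (1.751 + 1.960) × 0.980 − 1.960 = 1.676, so power ≈ .953.

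As a second form, take a joint-significance test of two paths assumed equally powered: each path has power √p at 350, is scaled in the same way, and the result is squared.

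| Assumed two-sided alpha | .79 at 336, single / joint | .96 at 336, single / joint |
|---|---|---|
| .10 | .775 / .770 | .954 / .952 |
| .05 | .774 / .768 | .953 / .952 |
| .01 | .770 / .763 | .952 / .950 |

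The loss is about 1.5 to 2.7 percentage points at the low end of the range and 0.6 to 1.0 at the high end. The third decimal only shows how little the assumptions matter; it is not real precision.

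**Step 6. What prior retention would imply.** 420 × 0.87 = 365 and 420 × 0.92 = 386. At alpha .05 the low end of the power range becomes .807 (single) or .812 (joint) at 365, and .828 or .839 at 386.

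**The case against.** The strongest reply is that nothing of substance follows. The gap is 14 men. The low end of the stated power is already below .80, so the correction does not push it across that conventional mark. The only retention experience in the documents is better than the planning assumption: a loss of 8–13% over three months, against a study meant to finish in under six weeks. On those figures 420 leaves 365 to 386 men, and power would be slightly above the stated range's low end. On this view the 20% is a cautious allowance, clumsily applied, and not a sign that the study will be underpowered.

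Most of that stands, and it is why the point is minor. It does not reconcile the figures. The sample-size section plans on 20%, not on past retention, and the Retention section does not say whether the earlier studies included a laboratory visit with alcohol administration. If the sponsor trusts the better retention, the 20% is the figure to change.

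A second reply is that the power loss rests on assumptions. That is also fair: alpha is assumed, and the joint-test figures assume equally powered paths. What can be supported is a loss of roughly 1 to 3 points. The finding itself, that 80% of 420 is not 350, needs none of those assumptions.

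**Conclusion.** The concern holds as an arithmetic error of minor consequence. The 350, the 20% and the 420 are mutually inconsistent, and the stated power belongs to a sample 14 men (4%) larger than the plan's own attrition rate delivers. This conclusion assumes only that attrition means the share of recruited men who are lost.

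The effect on power is small under every assumption tried: the low end of the range falls from .79 to between .76 and .78, and the high end from .96 to about .95. These are scaled approximations, not a rerun of the sponsor's simulation. No endpoint, design feature or analysis is affected.

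**What to change.** Correct one of the three figures.

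1. **Preferred: keep 420 and 20%.** State that 336 men are expected in the laboratory analysis, rerun the existing Monte Carlo simulation at 336 and report that power. This keeps both the recruitment target and the planning assumption. Cost: one sentence and one rerun, with reported power lower by roughly 1 to 3 points.
2. **Keep 420 and 350, and restate the attrition.** Say that 420 recruited yields 350 provided no more than 70 men (16.7%) are lost, and cite the prior retention and the short study duration in support. Because 16.7% is solved backwards from 420, the sponsor should first confirm that the earlier studies are comparable, in particular that they included a similar laboratory visit. Cost: one sentence.

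If the sponsor wants both 20% attrition and 350 completers, the recruitment figure is 438, or 18 more men. That is not needed to put the statement right.
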